### **4.4 Respiratory Care**

As described previously (Section 1.2.8), four adult patients developed pulmonary adverse events, possibly due to concurrent treatment with saracatinib. The development of any pulmonary symptom, no matter how minimal it may be, must be investigated immediately. Patients who have cough or slight discomfort in association with an upper respiratory infection may be monitored clinically, if the symptoms resolve or improve within a period of seven days.

Any patient who develops a pulmonary symptom, or has worsening of symptoms, will undergo thoracic CT as soon as possible. Pulmonary symptoms include, but are not limited to the following: cough, dyspnea, pain, hemoptysis, or oxygen saturation <94%. Oral therapy will be stopped immediately and the algorithm below should be followed.

If any of the following (cough, dyspnea, new pulmonary radiologic abnormality) occur or worsen while on study and cannot categorically be clinically ascribed to a cause other than saracatinib dosing, then

Interrupt saracatinib dosing

Perform a \*CT scan of the thorax  
Consider \*HRCT if necessary to rule out interstitial lung disease  
(defined as bilateral, diffuse, parenchymal lung disease)

CT scan of the thorax  
**DOES NOT** show interstitial lung disease  
(bilateral, diffuse, parenchymal lung disease)

CT scan of the thorax  
**DOES** show interstitial lung disease  
(bilateral, diffuse, parenchymal lung disease)

Consider re-commencing saracatinib dosing

Permanently discontinue saracatinib dosing

Begin appropriate management  
(Consider initiation of steroid therapy if non-drug related etiologies have been excluded)  
(Referral to a pulmonologist is recommended)

\*CT scan of thorax to be performed with slice thickness  $\leq 5$ mm

\*HRCT scan recommended parameters:

position	supine
slice thickness	$\leq 1.25$ mm
slice spacing	10 mm
start location	10 mm below the apices
end location	10 mm above costophrenic angles

#### 4.5 List of Contra-Indicated Medications

Saracatinib is substrate of CYP3A4 in humans. There are many drugs that either inhibit or induce CYP3A4 metabolism. This may result in increased or decreased exposure to saracatinib. The following tables list the drugs that are contra-indicated. In addition, the tables also list the minimum time period that the contra-indicated drug must be stopped, prior to the initiation of oral therapy with saracatinib or placebo.

Potent CYP3A4 inhibitors (may result in a 3-fold increase in exposure to saracatinib)

Contraindicated Drugs	Minimum period of discontinuation
Diltiazem	14 days
Clarithromycin (250 mg or 500 mg bid)	7 days
Erythromycin	7 days
Fluconazole 400 mg - lower doses (200 mg and 100 mg) are allowed	7 days
Itraconazole	7 days
Voriconazole	7 days
Ketoconazole	7 days
Indanavir	2 days
Nefazodone	2 days
Ritonavir	2 days
Saquinavir	2 days

Potent CYP3A4 inducers (may result in a 3-fold decrease in exposure to saracatinib)

Contraindicated Drugs	Minimum period of discontinuation
Barbiturates	14 days
Carbamazepine	14 days
Phenytoin	14 days
Rifabutin	14 days
Rifampicin	14 days
St John's Wort	14 days

Saracatinib is a moderate inhibitor of CYP3A4 in humans. There are many drugs that are CYP3A4 substrates. Therefore, patients who are receiving saracatinib may have increased exposure, pharmacological action or toxicity to CYP3A4 substrate medications due to inhibition of CYP3A4 by saracatinib. The following table lists the drugs that are contra-indicated. In addition, the table also lists the minimum time period that the contra-indicated drug must be stopped, prior to the initiation of oral therapy with saracatinib or placebo.

Contraindicated Drugs	Minimum period of discontinuation
Carbamazepine	14 days
Alfentanil	7 days
Cyclosporin	7 days
Tacrolimus	7 days
Atorvastatin	7 days
Lovastatin	7 days
Simvastatin	7 days

In addition, all of the medications listed above should not be restarted until 14 days after the last dose of oral therapy with saracatinib or placebo. They should never be restarted as long as the patient remains on oral drug therapy.

#### **4.6 Use of Concomitant Medications**

The following table is a list of medications that are moderate inhibitors of CYP3A4. It is possible that the concomitant use of these items may result in an increase in exposure to saracatinib. If possible, these medications should be avoided. However, they are not contra-indicated, but care must be taken to monitor closely for possible drug interactions.

Moderate CYP3A4 inhibitors (may result in an increase in exposure to saracatinib)

Drugs with possible interactions	
Fluconazole (200 mg or 100 mg) - 400 mg is contraindicated	Monitor closely
Verapamil	Monitor closely
Nelfinavir	Monitor closely

The following table is a list of medications that are CYP3A4 substrates, but are allowed to be taken in conjunction with oral therapy with saracatinib or placebo. Again, when at all possible, these drugs should be avoided, due to the possibility of increased exposure to these drugs. The following is a list of some medications that may be affected by saracatinib that may be more commonly used in this study population.

Drugs with possible interactions	
Alprazolam Midazolam Triazolam	Monitor closely
Felodipine Isradipine Nifedipine Other calcium antagonists	Monitor closely
Methylprednisolone	Monitor closely
Pimozide	Monitor closely
Quinidine	Monitor closely

This list is by no means complete. Treating physicians should determine the toxicity and interaction profile of all medications that her/his patient is taking.

#### **4.7 List of Contra-Indicated Foods**

The following is a list of food products that are moderate inhibitors of CYP3A4. It is possible that the concomitant use of these items may result in an increase in exposure to saracatinib. The following food products must not be taken while the patient is on study: grapefruits, grapefruit juice, star fruits, Seville oranges (also known as Chinese Bitter Oranges) and Seville orange marmalade.

## **5 Data Collection and Evaluation**

### **5.1 Data Collection**

This is a multi-institutional study. The data from all participating institutions will be stored electronically at the Michigan Institute for Clinical and Health Research (MICHR). Specific forms for registration, adverse event reporting, non-adverse event data collection, and documentation of shipment and receipt of biological specimens will be developed by SARC and the study Principal Investigator. The data manager at participating institutions will complete these online forms. Patients will be identified by their unique patient identification number on these forms. Only persons directly involved in this clinical trial will have access to the data stored at MICHR.

Electronic case reports are available at: <https://velos.med.umich.edu/eres/jsp/ereslogin.jsp>

Please contact the SARC Operations Office with any questions.

SARC Research Project Manager  
[name]  
[name]  
[name]  
[name]  
[contact]  
[contact]  
Email: [contact]

Required forms should be submitted electronically within two weeks of the required visit (see Section 3.4). The SARC Research Project Manager will review the receipt of all required forms and contact any institution directly if data entry is delinquent.

In addition to electronic data submission, participating institutions will print copies of completed forms, which will be kept with source documentation, in the patient study binder.

## **5.2 Toxicity Criteria**

Toxicity will be graded according to the CTEP CTCAE version 3.0 for toxicity and adverse event reporting. A copy of the Common Terminology Criteria for Adverse Events Version 3.0 (<http://ctep.cancer.gov/forms/CTCAEV3v3.pdf>) is available and is included in the study database. All appropriate treatment areas should have access to a copy of this document. Dose modifications will be made based upon the parameters defined previously (see Section 3.3.1).

## **5.3 Statistical Considerations**

The primary goal of this study is to determine whether the addition of saracatinib to surgery will result in an improvement in progression free survival (PFS). The sample size will be based on being able to detect a 60% relative improvement (from 33% to 53%) in PFS probability at two years. The current 2-year PFS probability is 33%, when a second surgical complete remission is achieved (3). Assuming exponential survival curves, the hazard rate corresponding to this 2-year PFS probability for the control arm is 0.0462, which is defined as approximately a 0.0462 probability of failing each month when the 2-year PFS probability is 33%. If we assume that the 2-year PFS probability may be 53% for the saracatinib arm, the hazard is 0.0265, which then results in a hazard ratio of 1.75. Forty-four patients will need to be randomized in each arm of the study, for a total of 88 patients, over a 48-month accrual period. Follow-up of the last patient randomized must continue for an additional year. Since this study follows a phase II.5 design (35), this provides 80% power to detect a difference between the two resulting actuarial curves with a one-sided 0.10 alpha level log-rank test.

A secondary goal of this study is to determine whether the addition of saracatinib to surgery will result in an improvement in overall survival (OS). The sample size selected to evaluate PFS will also be adequate to detect a 56% relative improvement (from 45% to 70%) in OS probability at three years. The current 3-year OS probability is 45%, when a second surgical complete remission is achieved (3). Assuming exponential survival curves, the hazard rate corresponding to this 3-year OS probability for the control arm is 0.0222, which is defined as approximately a 0.0222 probability of failing each month when the 3-year OS probability is 45%. If we assume that the 3-year OS probability may be 70% for the saracatinib arm, the hazard is 0.0099, which then results in a hazard ratio of 2.24. Evaluation of the 88 patients who are randomized, over the same time frame, will provide 85% power to detect a difference between the two resulting actuarial curves with a one-sided 0.10 alpha level log-rank test.

As explained in section 3.2.6, a subset of patients who recur while receiving placebo will be given the opportunity to receive saracatinib. Since patients on both arms will have received this agent, although at different times in the natural history of their disease, this may result in a lessening of the difference in survival between the arms compared to the case when only patients on one arm received the agent. However, since development of a recurrence may still be associated with overall survival duration, the magnitude of the impact may be limited.

An additional secondary goal is to determine if the addition of saracatinib to pulmonary metastasectomy, versus placebo and pulmonary metastasectomy, results in an increase in the time to treatment failure (TTF). Any adverse event that results in discontinuation of either saracatinib or placebo will be considered a treatment failure. This includes toxicity, disease progression or death.

Again, the randomized nature of the Phase II.5 study will allow us to determine the actual 2-year PFS and 3-year OS rates in patients who receive surgery and placebo, or surgery in combination with saracatinib.

Patients will be stratified based on the following criteria:

Number of Recurrences: FIRST versus SECOND versus THIRD or MORE

Number of Recurrent Nodules: ONE or TWO versus THREE or MORE

The date that the patient is randomized will be used as the starting date for measurements of overall survival, progression free survival and time to treatment failure. Progressive disease will be defined as recurrence of osteosarcoma based on radiographic evidence or histologic verification of the recurrent lesion.

At the first annual opportunity following the point at which 20 patients per arm have been randomized (40 total) and potentially followed for at least 12 months, an interim evaluation for futility will be performed.

The futility evaluation will be performed as follows. Based upon the full data available at that time, a conditional power analysis will be performed to determine if the trial is

unlikely to find an effect at the 0.10 one-sided level with continued accrual, based on the PFS endpoint. Since the goal is to detect a difference between two year PFS of 33% and 53%, an early evaluation will be performed based on the binomial probabilities at the 12-month point, which reflect the same objective. A PFS of 33% at 2 years would be equivalent to a 1 year PFS of 57.4% and a PFS of 53% at two years is equivalent to a 1 year PFS of 72.8%. Using these as the values under the alternative, and using the actual proportions without progression at 1 year based on the observed fractions based on the expected sample size at 1 year, the conditional power of the trial assuming accrual of however many patients would remain to be entered will be computed. If the conditional probability of finding a difference at the one-sided 0.10 level at the end of the trial is less than 20%, then it will be reasonable to recommend that no further patients will be enrolled. Alternatively, an evaluation based on exponential distribution of PFS may be substituted for the binomial evaluation.

At the first annual point after which 30 patients per arm (60 total) have been accrued and potentially followed for at least 12 months, a very stringent interim monitoring rule will be used to determine if superiority is identified early. If at this single interim efficacy evaluation for superiority, the log-rank p-value for the difference (one-tailed) is  $<0.001$ , then accrual will stop. Otherwise, enrollment will continue as planned.

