## **1.2 Background and Rationale**

### **1.2.1 Recurrent Osteosarcoma**

Osteosarcoma is the most common malignant bone tumor in the United States and Europe. Historically, this was once a fatal diagnosis. However, with the increasing use of chemotherapy in the late 1970s, patients who underwent both surgery and chemotherapy had a marked improvement in survival. Currently the overall cure rate is 65%, representing a dramatic improvement over previous decades (1,2). Unfortunately, patients who recur with disease have only a 25% five-year survival rate (3,4). Approximately 33% of patients who have completed therapy for osteosarcoma will recur. In large retrospective analyses performed by the Cooperative Osteosarcoma Study Group (3) and the Rizzoli Institute (4), the only patients who survived long-term were those who achieved complete surgical removal of recurrent tumor, illustrated in the survival curve

on the right (3). Specifically, 291 patients did not achieve surgical remission, and none of these patients survived long-term. In contrast, 512 patients achieved surgical remission and five-year overall survival rates were 38% and 30% in the two studies. These patients received either multi-agent, single agent or no chemotherapy, but they shared the common feature that everyone had achieved a second surgical remission. It did not appear that the addition of adjuvant treatment increased survival (40% survival with chemotherapy versus 35% survival without chemotherapy,  $p=0.35$ ) (3). However, this trend may eventually prove to be statistically significant in larger cohorts. Conversely, for those treated with chemotherapy or radiation therapy only without surgery, there were no survivors (4).

One of the significant prognostic factors that predicts for long-term survival is the number of nodules at the time of recurrence. In the Cooperative Osteosarcoma Study Group study, patients who had one nodule had a 38% 5-year overall survival rate, compared to 15% for patients with two or more nodules ( $p<0.01$ ) (3). Comparably, in the Rizzoli Institute study, patients who had one or two nodules had a 44% 5-year event free survival rate, compared to 22% for patients with three or more nodules ( $p<0.01$ ) (4).

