## 2.3 Patient Enrollment

[figure not shown]
A signed informed consent document will be obtained prior to entry onto the study. Following consent, patient information is entered in the eCRF database. All patients must have histological verification of recurrent osteosarcoma in the lung prior to randomization. A copy of the pathology report documenting histologic confirmation should be sent to the SARC RPM prior to randomization.

Enrollment will be centrally managed by the trial coordinating center, SARC. Patient data will be entered electronically by the participating institutions through the study website:

<https://velos.med.umich.edu/eres/jsp/ereslogin.jsp>

Each patient will be assigned a patient identification number automatically following enrollment. Patients can be enrolled at any time of the day, any day of the week, via the website.

Once the patient has undergone complete surgical resection and the institutional PI determines that all of the criteria for inclusion have been met per protocol Section 2.1, the eligibility CRF will be completed in the database. The patient can then be randomized.

Patients will be registered and then stratified based on the number of recurrences (FIRST versus SECOND versus THIRD or MORE) and the number of recurrent nodules (ONE or TWO versus THREE or MORE).

SARC will possess separate randomization sheets for each stratum. Patient treatment assignment will be kept confidential and will not be shared with the treating physician(s) or any other site team staff involved in the care of the patient, except in the event of a medical emergency where unblinding is necessary to ensure patient safety (See Operation Manual for details), or at the time of recurrence if the recurrence is in the lung. (See Section 7.4.2).

Any questions regarding eligibility or the randomization process can be addressed to the SARC Operations Office:

SARC Research Project Manager  
[name]  
[name]  
[name]  
[name]  
[contact]  
[contact]  
Email: [contact]

SARC, the study Principal Investigator and the Principal Investigators at each participating institution will have access to this website to review data regarding this clinical trial.

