### **3 Study Implementation**

#### **3.1 Study Design**

The primary objective of this study is to determine whether pulmonary metastasectomy and treatment with saracatinib, versus pulmonary metastasectomy and treatment with placebo, results in an increase in progression free survival. A secondary objective is to determine whether pulmonary metastasectomy and treatment with saracatinib, versus pulmonary metastasectomy and treatment with placebo, results in an increase in overall survival. Patients will be eligible for the study following the histological verification of recurrent osteosarcoma. Patients will be stratified based on the number of recurrences (FIRST versus SECOND versus THIRD or MORE) and the number of recurrent nodules (ONE or TWO versus THREE or MORE).

Randomization will occur following complete resection of all lung nodules and the histological verification of recurrent osteosarcoma.

Patients who are randomized to the saracatinib arm will receive saracatinib, 175 mg, orally, once daily, for a 28-day cycle, with no breaks between cycles. The total duration of treatment with saracatinib will be **thirteen 28-day cycles** (364 days total). Patients will receive one 125 mg tablet (9.5 mm diameter) and one 50 mg tablet (7 mm diameter).

Patients who are randomized to the placebo arm will receive placebo, orally, once daily, for a 28-day cycle, with no breaks between cycles. The total duration of treatment with placebo will be **thirteen 28-day cycles** (364 days total). Patients will receive one 9.5 mm tablet and one 7 mm tablet. These tablets will be indistinguishable from saracatinib.

Patients who recur in the lung while on-study and who are thought to be completely resectable will be unblinded. Those patients who were receiving placebo will be offered the opportunity to undergo additional surgical resection, followed by treatment with Saracatinib. If fully resected, they will then begin oral therapy with saracatinib. Saracatinib will be administered as a once daily, oral dose of 175 mg, for a 28-day cycle, with no breaks between cycles. The duration of treatment with saracatinib will be thirteen 28-daycycles (364 days total).

Patients will be followed for the duration that this study is open. If accrual rates proceed as projected, the total duration of this study will be six years.

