### 5.3.1 Patient Randomization

Details of patient randomization are described in the Operations Manual.

[name], the NCI statistician, will generate randomization assignment sheets. The sheets will be based on a stratified randomization, which will be created using software that generates randomized blocks of varying sizes as directed by [name]. He will provide these sheets directly to the SARC Operations Office, where they will be maintained in a confidential manner.

After the patient is registered and enrolled electronically by the site through the SARC study website, the site will contact the SARC Operations Office to obtain patient randomization treatment assignment.

The site pharmacy will be notified of the assigned randomization treatment (i.e. saracatinib or placebo). After confirmation of receipt of treatment assignment by the site pharmacy, labeled, blinded medication will be dispensed for the patient. This will consist of saracatinib in 125 mg and 50 mg tablets, or placebo 125-like and 50-like tablets, in accordance with the protocol.

The randomization assignment should be kept confidential and should not be shared with the treating physician(s) or any other site team staff involved in the care of the patient, except in the event of a medical emergency where unblinding is necessary for patient care (see section 7.4) or for disease recurrence (see section 7.4.2)

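### Optional small improvement: section 5.3 could specify the final PFS and OS log-rank tests as stratified by nodule count, a factor already used to stratify randomisation

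*Combined protocol and SAP*

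**What the plan says.** Section 3.1 states "Patients will be stratified based on the number of recurrences" (first, second, third or more) and on the number of nodules (one or two, three or more). That makes 3 × 2 = 6 cells. Section 2.3 adds "SARC will possess separate randomization sheets for each stratum", and section 5.3.1 says "The sheets will be based on a stratified randomization".

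Section 5.3 sizes the trial on PFS: 2-year PFS of 33% v 53%, 88 patients, 48 months of accrual and 12 more of follow-up. It states that "this provides 80% power to detect a difference between the two resulting actuarial curves with a one-sided 0.10 alpha level log-rank test". The OS paragraph uses the same kind of test and claims 85% power. The single interim superiority look stops accrual if "the log-rank p-value for the difference (one-tailed) is" below 0.001. The same section repeats the factors ("Patients will be stratified based on the following criteria") without linking them to any test. No section names a stratified log-rank test or an adjusted model.

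Section 1.2.1 reports that nodule count is prognostic. In one series, patients with "one or two nodules had a 44% 5-year event free survival rate, compared to 22% for patients with three or more nodules", which is the protocol's own cut. In the other, "patients who had one nodule had a 38% 5-year overall survival rate, compared to 15% for patients with two or more nodules".

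**The concern.** When the arms are balanced by design on a prognostic factor, the treatment difference varies less from trial to trial than an unstratified log-rank test assumes. The test then rejects less often than its nominal level under the null. This trial chose a one-sided 0.10 level because patients are rare (section 1.2.9), so leaving part of that 0.10 unspent has some cost.

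The silence in 5.3 also leaves three readings open: unstratified, stratified by nodules, or stratified by all six cells. With 88 patients these can give different p-values.

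**Working it through.** **Plan's own figures.** Exponential hazards: −ln(0.33)/24 = 0.0462 and −ln(0.53)/24 = 0.0265 per month, ratio 1.746. With uniform accrual over 48 months plus 12, the event probability per arm is 1 − [exp(−12λ) − exp(−60λ)]/(48λ), which gives 0.769 and 0.588. Events: 44 × 0.769 + 44 × 0.588 = 59.7.

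PFS power (Schoenfeld): Φ(½√59.7 × ln 1.746 − 1.2816) = Φ(0.872) = 0.808. Freedman's formula gives 0.793 and an exponential-rate comparison 0.803. The stated 80% is reproduced. For OS, with ratio 2.24 and 36.2 events, Freedman gives 0.846 and the exponential-rate comparison 0.851, against a stated 85%. None of these formulas contains strata.

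**Prognostic strength (section 1.2.1, exponential hazards assumed).** Nodules at the protocol's cut: ln(0.22)/ln(0.44) = 1.84. Relapses, from long-term survivor proportions of 30.6%, 25.9% and 16.7%: ln(0.259)/ln(0.306) = 1.14 and ln(0.167)/ln(0.306) = 1.51, the last resting on 2 of 12 patients.

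**PFS simulation.** 200,000 trials per setting and hypothesis, 88 patients, permuted blocks of 2 or 4 within the six cells, arm-level 2-year PFS held at 33% and 53%, one-sided 0.10. Block sizes, relapse mix and the share with three or more nodules are assumptions. Monte Carlo SE: 0.0007 for type I error, 0.09 points for power, 0.05 points for the paired difference. Entries are unstratified / nodule-stratified / six cells.

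| Nodule ratio; relapse mix; share with 3+ nodules | Type I error | Power % | Power % at equal size |
|---|---|---|---|
| 1.84; 72/23/5; 50% | 0.0926 / 0.1004 / 0.1017 | 80.60 / 81.95 / 80.41 | 81.73 / 81.90 / 80.13 |
| 1.84; 72/23/5; 30% | 0.0961 / 0.1020 / 0.1021 | 80.61 / 81.64 / 80.08 | 81.20 / 81.33 / 79.76 |
| 1.84; 60/30/10; 50% | 0.0941 / 0.1018 / 0.1024 | 80.52 / 81.83 / 80.26 | 81.49 / 81.56 / 79.82 |
| 1.4 (relapses 1.1, 1.25); 40% | 0.0999 / 0.1021 / 0.1021 | 80.66 / 80.62 / 78.91 | |
| No prognostic effect; 50% | 0.1019 / 0.1011 / 0.1018 | 80.29 / 79.75 / 78.03 | |
| No prognostic effect; 30% | 0.1010 / 0.1012 / 0.1008 | 80.62 / 80.03 / 78.44 | |

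Stratifying by nodules changes PFS power by +1.35, +1.03 and +1.31 points at ratio 1.84, by −0.04 at 1.4, and by −0.54 and −0.59 with no effect. At equal size the gains at 1.84 are +0.17, +0.13 and +0.07.

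A second simulation (blocks of 4, mix 60/25/15, 50% with three or more nodules) gave type I error 0.091 v 0.099 and power 80.7% v 82.0% at ratio 1.84. With no prognostic effect the loss was 0.6 to 0.9 points, hence an allowance of up to about 1.

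**Six cells.** These cost 0.2 to 0.5 points against the unstratified test at ratio 1.84, and about 2.2 with no effect. Section 1.2.1's relapse counts (173, 54, 12; total 239) put 12/239 × 88 = 4.4 patients in the third-or-more level, about 2.2 per nodule cell, or 3.1 and 1.3 if 30% have three or more nodules.

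**OS simulation (no cross-over modelled; unstratified v nodule-stratified, 50% with three or more nodules).** Ratio 1.96 = ln(0.15)/ln(0.38): type I error 0.0941 v 0.1012, power 87.39% v 88.03%, at equal size 88.06% v 87.90% (−0.16). Ratio 1.84: power 87.08% v 87.62%. No effect: 86.62% v 86.40%.

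**Interim look.** The 60th patient enters at 60/88 × 48 = 32.7 months; adding 12 gives 44.7, so a look at month 48 is assumed. With the documents' ratios, type I error at 0.001 is 0.0009 v 0.0012 (SE 0.0001), and the chance of stopping under the alternative is 10.3% v 11.6%. With no effect the latter is 10.8% v 10.4%.

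**The case against.** The strongest reply is that nothing is broken. An unstratified log-rank test after stratified randomisation is legitimate, the stated power is right, and section 1.2.9 itself calls the results not definitive. A type I error of 0.093 in place of 0.10 misleads nobody. All of this stands, and it is why the point is optional.

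It is also fair to say that the benefit is mostly a higher rejection rate under the null. At equal size the PFS gain nearly vanishes and the one OS comparison goes slightly the other way. Some stratified type I errors (0.1018 to 0.1021) sit a little above 0.10.

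The prognostic input is not secure either. Section 1.2.1 does not say the 44% v 22% comparison is limited to completely resected patients, and only such patients are randomised. The 38% v 15% comparison is weaker: its cut is one v two or more, and it cannot be confined to resected patients. The protocol gives 5-year OS after surgical remission as 38% and 30% in the two series. The 30.6% in the relapse breakdown identifies the 30% as the second series, so resected patients in the first had 38%. One-nodule patients in that same series also had 38%, so a resected group including multi-nodule patients at 15% would average less.

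What remains is that the plan randomises on a factor it reports as prognostic at its own cut and does not say whether the tests use it. Settling that costs almost nothing.

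**Conclusion.** A cheap, optional improvement; small, and not an error. If the nodule ratio is near 1.84 in this population, stratifying the PFS test moves the one-sided type I error from about 0.093 to 0.096 up to about 0.10 and adds about 1 point of power, almost entirely by removing conservatism. At 1.4 there is no gain. If nodules are not prognostic in resected patients, about 0.5 to 1 point is lost. The OS gain, about 0.5 points, is uncertain for the reasons above. The results assume exponential hazards and the stated stratum mixes and block sizes.

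A reader might infer more, and the documents do not support it:
- That the plan has chosen unstratified tests. It is silent; the tests are simply not specified as stratified.
- That the stated power is wrong or the test invalid. The power reproduces, and the unstratified test is valid.
- That stratifying calibrates the interim rule. The simulated level moves from 0.0009 to 0.0012 around 0.001, so no calibration gain is claimed there.
- That the analysis should use every randomisation stratum. Six cells are too sparse and do not help.

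**What to change.** In section 5.3, state that the primary PFS log-rank test, and for consistency the OS log-rank test, is stratified by nodule count (one or two v three or more) and not by the six combined cells. Specify the category recorded at randomisation, because section 2.2 leaves indeterminate nodules to clinical judgement and a later recount could differ. Report the hazard ratio from the matching stratified Cox model and keep the unstratified log-rank test as a sensitivity analysis. If the 0.001 interim look uses the same stratified test, say that this is for consistency only.

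Record the trade-off: about 1 point of PFS power and a type I error near 0.10 if nodules are as prognostic as section 1.2.1 suggests, up to about 1 point lost if they are not. Fix the choice before unblinding.

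Cost: one or two sentences. Nodule category is already recorded to randomise each patient, and neither the sample size nor the stated power changes.
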